3.1.2. Safety Primary Endpoints

Safety primary endpoints include both reactogenicity data and AEs.

The subsections below describe how to derive each safety endpoint.

3.1.2.1. Local Reactions and Systemic Events Within 7 Days After Vaccination

Reactogenicity (ie, local reactions and systemic events) will be reported via the enhanced e-diary with recalling period. Additionally, for any missed response in the e-diary or completely missing e-diary, participants will be asked by the investigator at the site visit to recall any experienced reactogenicity during the missed day(s). Temperature, size of redness, or size of swelling for those who experienced reactogenicity will all be recorded for those missing days.

Every participant who receives the study intervention will have the below variables derived:

1. Presence (yes or no) of each local reaction/systemic event on any day (Day 1 through Day 7):
 - = Yes, if the participant reports reaction as "yes" either from the e-diary or PRR during any day of Day 1 through Day 7;
 - = *No*, for the vaccinated participants who were not derived as "yes" in the above.
2. Presence (yes or no) of any local reaction/systemic event on any day (Day 1 through Day 7):
 - = Yes, if the participant reports "yes" either from the e-diary or PRR during any day of Day 1 through Day 7 for at least 1 local reaction/systemic event;
 - = *No*, for the vaccinated participants who were not derived as "yes."
3. Maximum severity of each local reaction/systemic event on any day (Day 1 through Day 7) after vaccination:
 - = *Highest grade* (maximum severity either from the e-diary or PRR) for the specific local reaction/systemic event from Day 1 through Day 7.
 - = 0, for the presence derived as "no."
4. Maximum severity of any local reaction/systemic event on any day (Day 1 through Day 7):
 - = *Highest grade* (maximum severity either from the e-diary or PRR) for any local reaction/systemic event from Day 1 through Day 7.
 - = 0, for the presence derived as "no."
5. Onset day of each local reaction/systemic event:

The onset day is the first day of reporting any severity of the specific local reaction/systemic event, either from the e-diary or PRR.

For the onset day of each local reaction/systemic event, if the participant reports changes in severity of the local reaction/systemic event, only the first day of reporting that specific local reaction/systemic event will be counted.
6. Duration of each local reaction/systemic event:

The duration of each local reaction/systemic event will be calculated in days as the resolution date of reaction – start date of reaction + 1. Resolution of the event is the last day on which the event is recorded in the e-diary or collected in the CRF.

If there is no known end date, the duration will be considered unknown and set to "missing." Participants with no reported reaction have no duration.

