8.3.4.2. Local Reactions

Following vaccination (where Day 1 is the day of vaccination), participants will be asked to assess redness, swelling, and pain at the injection site, and to record the symptoms in the e-diary or appropriate device daily.

Redness and swelling will be measured by the participant and recorded in measuring device units (range: 1 to 21; an entry in the e-diary of 21 will be denoted as ≥ 21), and then categorized during analysis as absent, mild, moderate, or severe based on the grading scale in [Table 5](#). Measuring device units can be converted to centimeters according to the following scale: 1 measuring device unit = 0.5 cm. Pain at the injection site will be assessed by the participant as absent, mild, moderate, or severe according to the grading scale in [Table 5](#).

If a severe (Grade 3) local reaction is reported in the reactogenicity e-diary, a telephone contact should occur to ascertain further details and determine whether a site visit is clinically indicated.

Only an investigator or a qualified designee is able to classify a participant's local reaction as Grade 4, after clinical evaluation of the participant, documentation from another medically qualified source (eg, emergency room or hospital record), or telephone contact with the participant. If a participant experiences a Grade 4 local reaction, the investigator must immediately notify the sponsor. A Grade 4 local reaction will be collected on the CRF.

If a local reaction persists beyond the end of the 7-day e-diary collection period, the participant will be requested to report that information and/or any new events that develop to the investigator or the study staff. The investigator will enter this additional information in the participant's source notes and CRF.

Table 5. Grading Scale for Local Reactions

	Mild (Grade 1)	Moderate (Grade 2)	Severe (Grade 3)	Grade 4^a
Redness	>2.0 cm to 5.0 cm (5 to 10 measuring device units)	>5.0 cm to 10.0 cm (11 to 20 measuring device units)	>10 cm Necrosis or exfoliative dermatitis	Necrosis or exfoliative dermatitis
Swelling	>2.0 cm to 5.0 cm (5 to 10 measuring device units)	>5.0 cm to 10.0 cm (11 to 20 measuring device units)	>10 cm Necrosis	Necrosis
Pain (at the injection site)	Does not interfere with activity	Interferes with activity	Prevents daily activity	Emergency room visit or hospitalization for severe pain at the injection site

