a. Only an investigator or qualified designee is able to classify a participant's local reaction as Grade 4, after clinical evaluation of the participant, documentation from another medically qualified source (eg, emergency room or hospital record), or telephone contact with the participant. Grade 4 local reactions will be collected on the CRF and assessed by the investigator or qualified designee.

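### Does SAP 3.1.2.1 leave redness or swelling of 1 to 4 units counted as present but without a severity grade?

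*SAP*

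**What the plan says.** SAP 3.1.2.1 lists the variables derived for every vaccinated participant. Under item 1 a given reaction is present: "Yes, if the participant reports reaction as 'yes' either from the e-diary or PRR during any day of Day 1 through Day 7". Item 2 applies the same rule to any local reaction or systemic event. Items 3 and 4 take the highest grade from either source, or else "0, for the presence derived as 'no". Item 5 fixes onset: "The onset day is the first day of reporting any severity of the specific local reaction/systemic event, either from the e-diary or PRR". Item 6 counts duration up to the resolution date: "Resolution of the event is the last day on which the event is recorded in the e-diary or collected in the CRF". None of these items states a size or cites a grading table.

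Protocol 8.3.4.2 has the participant measure redness and swelling, "recorded in measuring device units (range: 1 to 21; an entry in the e-diary of 21 will be denoted as" 21 or more, with one unit equal to 0.5 cm, "and then categorized during analysis as absent, mild, moderate, or severe based on the grading scale in" Table 5. In that table mild is ">2.0 cm to 5.0 cm (5 to 10 measuring device units"), moderate is 11 to 20 units and severe is above 10 cm. Grade 4 does not depend on size: "Grade 4 local reactions will be collected on the CRF and assessed by the investigator or qualified designee".

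Three other places bear on the point. Protocol Table 8 reports reactogenicity by highest grade and for any severity. SAP 2.1 declares no departure from the protocol's analysis. Protocol section 9 lets the SAP depart from the protocol where appropriate, but a major change to a primary endpoint definition or its analysis must also appear in a protocol amendment.

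**The concern.** The device scale allows entries that no grade covers. If presence is taken from the participant's 'yes' alone, someone whose redness never exceeds 4 units is present under item 1, falls below Grade 1 in Table 5, and cannot receive 0 under item 3 because 0 requires presence to be no. Nothing in SAP 3.1.2.1 resolves that state.

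Local reactions within 7 days are a primary safety estimand. If the any-redness or any-swelling row were built from the bare presence flag, it could exceed the sum of its severity rows, and the error could only push the rate upward. The combined row for any local reaction would move only where the small redness or swelling was the participant's sole local reaction. Two programmers, one working from the SAP section and one from the protocol section, could then report different rates from the same data.

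**Working it through.** **Inputs.** Entry range 1 to 21 and 0.5 cm per unit (Protocol 8.3.4.2); size bands (Protocol Table 5); derivation rules (SAP 3.1.2.1, items 1 to 6); group sizes 240 and 120 (Protocol Table 1).

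**Step 1: reproduce the Table 5 bands.** Size in cm = units × 0.5.

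- 1 to 4 units: 0.5 to 2.0 cm. Mild needs more than 2.0 cm, so no grade applies.
- 5 to 10 units: 2.5 to 5.0 cm, Grade 1.
- 11 to 20 units: 5.5 to 10.0 cm, Grade 2.
- 21 units: 10.5 cm or more, Grade 3.

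The unit and centimetre bands agree with each other.

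**Step 2: apply each reading to a participant's largest entry, with no Grade 4 classification.**

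| Largest entry | SAP items 1 and 3 read alone | Protocol 8.3.4.2 with Table 5 |
|---|---|---|
| none | no, 0 | absent, 0 |
| 1 to 4 units | yes, no grade defined | absent, 0 |
| 5 to 10 units | yes, 1 | mild, 1 |
| 11 to 20 units | yes, 2 | moderate, 2 |
| 21 units | yes, 3 | severe, 3 |

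The readings differ in one row only. The protocol reading fills every row, and its severity rows sum to its any row.

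**Step 3: ask which reading the documents support.** SAP 3.1.2.1 defines no grade for any event, so items 3 and 4 cannot be run without the protocol scales. The protocol sentence that sends the analyst to Table 5 is the same sentence that creates the absent category, so using the table's grades while ignoring that category would be selective. Items 1 to 4 also cover fever, which is collected as a temperature and defined in Protocol 8.3.4.4. A bare 'yes' does not define fever either, so the generic wording was never self-contained.

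**Step 4: size under the isolated reading.** Each affected participant adds 1/240 = 0.42 points (RSVpreF) or 1/120 = 0.83 points (placebo). The documents give no frequency, so these counts are assumptions:

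- 0 and 0 participants: 0 points in each arm.
- 2 and 1: 2/240 = 1/120 = 0.83 points in each arm.
- 6 and 3: 6/240 = 3/120 = 2.50 points in each arm.

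With equal proportions the difference between arms does not move. With 6 and 0 it would move by 2.50 points. For the interval, take an assumed 12/240 graded participants and use the Clopper-Pearson limits Beta(0.025; x, n−x+1) and Beta(0.975; x+1, n−x). This gives 5.00% (2.61 to 8.57). Adding 6 ungraded participants gives 18/240 = 7.50% (4.51 to 11.59), while the severity rows still sum to 5.00%. Mild, moderate, severe and Grade 4 counts are the same throughout.

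**Step 5: size under the protocol reading.** Zero.

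**Step 6: would a size threshold on onset and duration help?** Take 6 units on Days 3 and 4, then 2 units with a CRF stop date on Day 10. Duration is 4 − 3 + 1 = 2 days if diary days must reach 5 units, and 10 − 3 + 1 = 8 days if the CRF date is used as recorded. A threshold on the diary days but not on the CRF dates would create an inconsistency in summaries that are only supplementary and carry no confidence intervals.

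**The case for a change.** The best case for a change is that the SAP presents itself as the detailed methodology, and section 3.1.2 says its subsections describe how each safety endpoint is derived. A primary endpoint rule should not depend on which document the programmer opens. Protocol section 9 lets the SAP modify the protocol, so silence on size might be taken as a deliberate simplification. SAP 3.1.2.1 also speaks of recording sizes on missed days for people who had a reaction, which hints that the yes/no question comes before the measurement. The remedy would cost a sentence or two and need no new data.

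Part of this stands: SAP 3.1.2.1 does lack the cross-reference, and the two readings do diverge for 1 to 4 units. The inference that the SAP changed the rule does not stand. Protocol section 9 requires an amendment for a major change to a primary endpoint, Amendment 1 keeps the size categories, and SAP 2.1 disclaims any change. If counting small redness were too minor to need an amendment, it would also be too minor to matter here. The documents do not show how the e-diary produces a 'yes' for redness or swelling, and they do not say outright that the any row comes from the presence flag. Any severity in Protocol Table 8 is most naturally any grade.

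**Conclusion.** The concern identifies a real omission but not a defect in the analysis. Read together, the protocol and SAP give one workable answer: a largest reading of 1 to 4 units is absent with severity 0, a reading of 5 units or more is present with its Table 5 grade, and an investigator-classified Grade 4 reaction is present whatever its size. An analyst who programs the severity rows has to open Table 5 and meets that answer there. The isolated reading would also expose itself, because it yields participants who are present with no grade and severity rows that do not add up.

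The effect is zero under the protocol reading. Under the other it is 0.42 or 0.83 points per affected participant, at a frequency the documents do not give, in a descriptive study with no hypothesis test. The conclusion assumes that the analysts use the protocol's grading tables, and that the size categories were already in the original protocol to which the SAP is tied. The part of the amendment summary that is available lists no change to them. Naming Tables 5 and 7 in the SAP would be a courtesy to the programmer and would alter no result.

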8.3.4. Electronic Diary for Reactogenicity

Participants will be required to complete a reactogenicity e-diary through an application installed on a provisioned device or on the personal device of the participant. They will be asked to monitor and record prespecified local reactions, systemic events, and temperature daily for 7 days or longer following vaccination, where Day 1 is the day of vaccination. Participants will receive reminders to complete the reactogenicity e-diary on a daily basis, starting on the day of study intervention administration (Day 1) through Day 7, or longer if there are ongoing symptoms.

The e-diary allows recording of these assessments each day, thus providing an accurate representation of the participant's experience.

Data on local reactions, systemic events, and temperature recorded in the e-diary will be transferred electronically to the e-diary vendor, where they will be available for review by investigators, their qualified designees, and sponsor staff at all times via an internet-based portal. At intervals agreed to by the vendor and Pfizer, these data will be transferred

electronically to Pfizer for analysis and reporting. These data do not need to be recorded by the investigator in the CRF, except for the following conditions:

- Grade 4 local reactions will be collected in the CRF.
- Any local reactions or systemic events occurring within the first 30 minutes after study vaccination must be recorded on the CRF. The time of onset (relative to vaccination) must be recorded.
- If a participant withdraws because of prespecified event(s) recorded in the e-diary, the event(s) should be recorded on the CRF, regardless of whether the investigator considers the event(s) to be clinically significant.
- The investigator or designee must obtain stop dates for any symptoms ongoing on the last day, from Day 7 onwards until resolution. The stop dates should be documented in the source documents and the information entered in the CRF.

Investigators (or appropriately qualified designees) are required to review the e-diary data online at frequent intervals to evaluate participant compliance and as part of the ongoing safety review.

All provisioned e-diary devices must be collected per the study [SoA](#).

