8.3.4.3. Systemic Events

Following vaccination (where Day 1 is the day of vaccination), participants will be asked to assess fatigue, headache, vomiting, nausea, diarrhea, muscle pain, and joint pain, and to record the symptoms in the e-diary or appropriate device daily. The systemic symptoms will be assessed by the participant as absent, mild, moderate, or severe according to the grading scale in [Table 6](#).

If a severe (Grade 3) systemic event is reported in the reactogenicity e-diary, a telephone contact should occur to ascertain further details and determine whether a site visit is clinically indicated.

Only an investigator or qualified designee is able to classify a participant's systemic event as Grade 4, after clinical evaluation of the participant, documentation from another medically qualified source (eg, emergency room or hospital record), or telephone contact with the participant. If a participant experiences a Grade 4 systemic event, the investigator must immediately notify the sponsor. A Grade 4 systemic event will be collected on the CRF.

Further, if a systemic event persists beyond the end of the 7-day e-diary collection period, the participant will be requested to report that information and/or any new events that develop to the investigator or the study staff. The investigator will enter this additional information in the participant's source notes and CRF.

Table 6. Grading Scale for Systemic Events

	Mild (Grade 1)	Moderate (Grade 2)	Severe (Grade 3)	Grade 4^a
Fatigue (= tiredness in e-diaries)	Does not interfere with activity	Some interference with activity	Prevents daily routine activity	Emergency room visit or hospitalization for severe fatigue
Headache	Does not interfere with activity	Some interference with activity	Prevents daily routine activity	Emergency room visit or hospitalization for severe headache
Vomiting	1 to 2 times in 24 hours	>2 times in 24 hours	Requires IV hydration	Emergency room visit or hospitalization for severe vomiting
Nausea	Does not interfere with activity	Some interference with activity	Prevents daily routine activity	Emergency room visit or hospitalization for severe nausea
Diarrhea	2 to 3 loose stools in 24 hours	4 to 5 loose stools in 24 hours	6 or more loose stools in 24 hours	Emergency room visit or hospitalization for severe diarrhea

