5.3. Methods to Manage Missing Data

5.3.1. Safety Data

Standard algorithms for handling missing AE dates and missing AE severity levels will be applied as described in the safety rulebook summary.

Missing data handling rules on the safety data are described in detail in the corresponding endpoint sections.

The reactogenicity data are collected in the enhanced e-diary, which allows participants to enter data later if for some reason they missed an earlier opportunity to do so. Additionally, for any e-diary entries that are out of the window to reenter the information in the e-diary recollection period, the data will be collected onsite via PRR. Therefore, it is expected very few e-diary entries would be missing.

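### The maximum-severity rule does not name the CRF as a source, so on completed diary days a confirmed Grade 4 reaction (10 of 11 solicited items) would be tabulated at Grade 3 or lower (minor)

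*SAP*

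**What the plan says.** In SAP section 3.1.2.1, item 3 takes the maximum severity of each local reaction or systemic event as the highest grade, "maximum severity either from the e-diary or PRR) for the specific local reaction/systemic event from Day 1 through Day 7". Item 4 uses the same two sources for the maximum over any reaction or event.

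PRR appears in the SAP as a back-up to the diary. Section 3.1.2.1 says that "for any missed response in the e-diary or completely missing e-diary, participants will be asked by the investigator at the site visit to recall" what they experienced on the missed days. Section 5.3.1 adds that, for entries past the diary's re-entry window, "the data will be collected onsite via PRR".

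The protocol deals with Grade 4 separately from diary grading:

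- For the seven systemic symptoms other than fever, section 8.3.4.3 says: "The systemic symptoms will be assessed by the participant as absent, mild, moderate, or severe". Section 8.3.4.2 uses the same four levels for injection site pain, and for redness and swelling once the measured size is categorized.
- Sections 8.3.4.2 to 8.3.4.4 let only the investigator or a qualified designee assign Grade 4. The record goes to the CRF: "A Grade 4 local reaction will be collected on the CRF" and "A Grade 4 systemic event will be collected on the CRF". Fever follows the same route.
- Section 8.3.4 says that diary data generally need not be entered on the CRF, and then lists exceptions. One of them is: "Grade 4 local reactions will be collected in the CRF".

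SAP section 6.1.2.1 and Protocol Table 8 report reactogenicity by maximum severity within the primary safety analysis.

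**The concern.** The derivation reads from two sources, and the highest grade on the scale is held in a third. A programmer who follows items 3 and 4 as written never consults the CRF record that carries Grade 4. For most items a Grade 4 count of zero would then follow from the rule and would not be an observation.

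Two other statements in the SAP make this look like an oversight. Item 6 of the same section, on duration, does name the CRF as a source alongside the diary. Section 2.3 says that potential Grade 4 events will be assessed by the investigator or a qualified person, yet the severity derivation does not use the result.

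What is at stake is the top category of a primary safety table and bar chart in a study whose purpose is to describe safety.

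**Working it through.** The plan states no figure that depends on this rule, so there is nothing to reproduce. The check is a count of items, followed by an illustration of size.

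**Step 1. Items.** SAP section 2.2 lists 3 local reactions and 8 systemic events: 3 + 8 = 11.

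**Step 2. Highest grade reachable from a completed diary** (Protocol sections 8.3.4.2 to 8.3.4.4, Tables 5 to 7).

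| Items | Number | Diary entry | Highest diary grade | What defines Grade 4 |
|---|---|---|---|---|
| Redness, swelling | 2 | Size in device units | 3 | Necrosis; for redness also exfoliative dermatitis |
| Injection site pain | 1 | Four-level rating | 3 | Emergency room visit or hospitalization |
| Fatigue, headache, vomiting, nausea, diarrhea, muscle pain, joint pain | 7 | Four-level rating | 3 | Emergency room visit or hospitalization |
| Fever | 1 | Temperature | Value can fall in the Grade 4 range | Above 40.0°C |

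Items that stop at Grade 3: 2 + 1 + 7 = 10 of 11. This is the conservative count. If the investigator-only rule in section 8.3.4.4 is applied to fever as well, it is 11 of 11.

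The tabulated grade can be well below 3. Redness of 3 cm with necrosis is entered as 3 / 0.5 = 6 device units, which Table 5 grades as mild, while the confirmed grade is 4.

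**Step 3. Where such cases still appear.** SAP section 3.3.3 takes several reactogenicity endpoints from the CRF: immediate, leading to withdrawal, medically attended, and qualifying as an SAE.

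- Pain and the seven systemic symptoms (1 + 7 = 8 items) have a Grade 4 defined by an emergency room visit or hospitalization. They should appear as medically attended and, where serious, among the SAEs.
- Redness and swelling (2 items) appear there only if one of those conditions is also met.
- None of these endpoints carries the reactogenicity grade.

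**Step 4. Size.** The planned groups are 240 and 120 (Protocol section 9.5). Clopper-Pearson 95% limits are:

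- 0 events: upper limit = 1 − 0.025^(1/n)
- 1 event: lower limit = 1 − 0.975^(1/n); upper limit = 0.975 quantile of Beta(2, n − 1)

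| Group | Case omitted | Case counted |
|---|---|---|
| RSVpreF, n = 240 | 0/240: 0% (0 to 1.53%) | 1/240: 0.42% (0.01 to 2.30%) |
| Placebo, n = 120 | 0/120: 0% (0 to 3.03%) | 1/120: 0.83% (0.02 to 4.56%) |

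The documents give no Grade 4 rate. For assumed per-participant rates p, the chance of at least one case is 1 − (1 − p)^n:

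| Assumed p | n = 240 | n = 120 | n = 360 | Expected cases, 360 × p |
|---|---|---|---|---|
| 0.05% | 11.3% | 5.8% | 16.5% | 0.18 |
| 0.1% | 21.3% | 11.3% | 30.2% | 0.36 |
| 0.2% | 38.2% | 21.4% | 51.4% | 0.72 |

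**The case against.** **PRR is collected by the site and might carry an investigator's grade.** This cannot be excluded, because the SAP's abbreviations appendix is not in the text reviewed. It is why the point is limited to completed diary days. As described, PRR is used only where a diary entry is missing.

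**Protocol section 8.10.5 refers to a suspected Grade 4 event reported in the e-diary.** That fits poorly with the four-level scales. The section still requires a telephone contact or site visit to confirm Grade 4, so the diary entry is not the classification.

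**For redness and swelling the protocol itself stops the analysis categories at severe.** This is true of the measured size, and the SAP agrees with it. Table 5 nevertheless defines Grade 4 for both items and sends it to the CRF, and Table 8 asks for maximum severity.

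**The events are reported elsewhere.** This largely stands, as step 3 shows. Protocol section 10.2.3 also has the investigator rate the intensity of every AE and SAE, so serious cases are not without a grade. That scale is a different one: its Grade 4 means life-threatening.

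**Little depends on this row.** This stands too. There is no hypothesis test and no decision rule, and the assumed rates have no basis in the documents.

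A reader might also infer that onset days would be wrong, since item 5 has the same source limit: "The onset day is the first day of reporting any severity of the specific local reaction/systemic event, either from the e-diary or PRR". The documents do not support making much of this. On a completed diary day, a participant sent to the emergency room for pain or headache would have had to record the symptom as absent. The same reasoning applies to presence in items 1 and 2.

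**Conclusion.** The point holds as a minor one. Items 3 and 4 state a rule which, followed literally, would show a confirmed Grade 4 event at Grade 3 or lower for 10 of the 11 solicited items on completed diary days. This is more than missing detail, because the stated rule gives a result that conflicts with the protocol's grading.

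It rests on two assumptions: that PRR is used only as SAP sections 3.1.2.1 and 5.3.1 describe, and that programming follows the text. The number of cases affected is unknown and probably small; under the assumed rates, fewer than one is expected among 360 participants.

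A reader might infer that Grade 4 reactions would disappear from the report, or that the primary reactogenicity rates would be biased. Neither follows. Grade 4 pain and systemic events should still appear as medically attended or serious. The primary estimand is the percentage reporting each event whatever its grade, and that is essentially unchanged.

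**What to change.** Change SAP section 3.1.2.1, items 3 and 4 only. Suggested sense: *Highest grade from the e-diary, PRR, or an investigator-confirmed Grade 4 record on the CRF where Grade 4 was reached within Day 1 through Day 7; the investigator classification prevails for Grade 4.*

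The time limit should refer to when Grade 4 was reached and not to when the event began. Protocol sections 8.3.4.2 and 8.3.4.3 also send events that persist past the seven-day diary period to the CRF. An onset-based limit could therefore admit a Grade 4 first reached after Day 7.

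Apply the same precedence to fever, so that the tabulation of a diary temperature above 40.0°C is reconciled with Protocol section 8.3.4.4 and Table 7.

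Leave items 1, 2 and 5 as they are. Presence is the primary estimand's variable, which SAP section 2.2.1.2.1 ties to the diary items, and the case for changing onset is close to hypothetical.

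The cost is SAP wording and programming. The protocol already requires the Grade 4 record, so sites collect nothing new.
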